This is a study of an innovative multi-component intervention delivered in a real workplace. The primary outcome is change in VAT. The sample sizes herein were set based on data collected in our Pounds Lost51 study that showed baseline VAT to be approximately 5.43 kg and indicated that a 21% reduction in VAT (equivalent to 1.15 kg, SD=1.20kg) can be achieved with a suitable intervention. The nominal level of significance alpha = 0.05 will be used to compare mean VAT change (e.g., reduction) in WMPD vs CON, A minimum of 18 subjects per intervention who all complete protocol through end of study would conservatively provide at least 80% power for detecting significance where the underlying true differential intervention change in VAT is at least 1.15 kg. We have planned for 20 participants per group (total n = 41) in this study to allow for 10% attrition. As designed, this study will clearly inform the feasibility of combining these components of a workplace multi-component energy expenditure intervention.

b. Data Management:

The data management will be conducted by the Pennington Biomedical Research Computing Group. There will be limited access to all data including locked cabinets for paper files and password protected computers for electronic data. The PBRC has a fully integrated, campus-wide, automated, data management system. All data are entered into a Central Database using existing methodology that has been fully validated and undergoes continuous quality assurance by the PBRC Research Computing Core and NORC. Most data are automatically uploaded from the instruments that measure the endpoint. All self-report inventories will be scanned and scored automatically using the Psychological Assessment Laboratory's optical scanning system, which automatically uploads the data into the Central Database. Exercise testing data will be downloaded from the Parvo Medics' TrueOne® 2400 cart directly following each test and reviewed for integrity. All data are backed-up daily and the Research Computing Core at the PBRC oversees all data management.

c. REDCap Database:

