On study change in MRI-determined VAT, weight, waist circumference, fasting glucose and insulin, HOMA-IR will be summarized by intervention group as means and 95% confidence intervals in an intention-to-treat analysis of (1) all participants and (2) the subset of participants who achieve the highest tertile of adherence to the intervention. Linear models will provide the primary framework for significance testing. In the analysis of VAT (the primary outcome), statistical significance of differential longitudinal changes in response to intervention (WMPD vs CON) will be assessed employing repeated measures mixed effects models with maximum likelihood estimation and Kenward-Rogers adjustment to the degrees of freedom in an intention-to-treat analysis of (1) and (2) for each outcome measure using all available data. Study arm (WMPD. or CON), age, race, sex and interactions will be taken as having fixed effects; participants within groups will be considered as having random effects. Covariates such as age, sex, race and baseline assessment of VAT will be included in preliminary models and retained in final analytic models if warranted. The model residual covariance structure (e.g., unstructured, compound symmetric, auto-regressive) across time will be investigated to enhance efficiency of statistical tests. Secondary outcomes, such as on-study changes in weight, waist circumference, fasting glucose, insulin, and HOMA_IR will be analyzed using statistical models analogously to the approach described for the primary outcome.] Results for each outcome will be summarized as least squares means and 95% confidence intervals for each intervention across the assessment times. Model residuals will be tested to see if they have distributions that are approximately Gaussian and data transformations will be performed if needed. Group differences in baseline characteristics will be tested and corrective steps, such as post-stratification and adding model covariates will be employed as necessary Null hypotheses will be tested against two-directional alternatives at the nominal 0.05 significance level using Bonferroni adjusted p-values when appropriate. All statistical analyses will be performed using statistical software in SAS version 9.3.

X. References

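### Fitting the primary VAT model by maximum likelihood with about 36 completers makes the 5% test run at about 5.6%; REML corrects this, and the primary covariate list should be fixed in one statement

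*Combined protocol and SAP*

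**What the plan says.** Section IX.d (Data Analysis) fits the primary VAT analysis with "repeated measures mixed effects models with maximum likelihood estimation and Kenward-Rogers adjustment to the degrees of freedom". The model language is that of a two-visit analysis: participants have random effects, the residual covariance across time is to be explored, and results are reported as "least squares means and 95% confidence intervals for each intervention across the assessment times". On the error rate, "Null hypotheses will be tested against two-directional alternatives at the nominal 0.05 significance level". Section IX.a (Sample size and statistical power) agrees: "The nominal level of significance alpha = 0.05 will be used to compare mean VAT change". It plans for "A minimum of 18 subjects per intervention who all complete protocol through end of study".

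On covariates, Section IX.d makes three statements. It first takes study arm, age, race, sex and unnamed interactions as fixed effects. It then makes age, sex, race and baseline VAT conditional: "baseline assessment of VAT will be included in preliminary models and retained in final analytic models if warranted". Finally, "Group differences in baseline characteristics will be tested and corrective steps, such as post-stratification and adding model covariates will be employed as necessary". Neither the second nor the third statement gives a criterion. The secondary outcomes "will be analyzed using statistical models analogously to the approach described for the primary outcome", and the primary analysis is also repeated in the participants in the top third of adherence.

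**The concern.** ML estimates a variance by dividing the residual sum of squares by the number of observations, with no allowance for the mean parameters fitted. In a large trial this is invisible. With 36 completers it makes the standard error too small, so the test rejects more often than the stated 5% and the interval covers less than 95% of the time. REML makes the allowance. The Kenward-Roger method is usually paired with REML. It changes the reference degrees of freedom and applies a small-sample covariance correction, and the question is whether that undoes the ML bias.

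The covariate wording raises a separate matter. The same section both fixes and leaves open whether age, race and sex are in the model, so the primary analysis is not uniquely defined before month-3 data are seen.

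**Working it through.** **Inputs.** From Section IX.a: SD 1.20 kg (taken as the SD of change), difference 1.15 kg, 18 completers per arm (36 in all), alpha 0.05. Section IX.d makes the test two-sided. The documents do not give the correlation between baseline and month-3 VAT, so it is assumed where needed (0.5 to 0.95).

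**1. The plan's own figure.** The normal approximation gives n per arm = 2 × 1.20² × (1.960 + 0.842)² / 1.15² = 17.1, rounded up to 18. Dividing 18 by 0.90 gives 20. Both planned numbers reproduce. Power at 18 per arm is 82.0% by the normal approximation and 79.8% by the noncentral t with 34 df.

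**2. The ML standard error.** With complete two-visit data and an unstructured covariance, the arm-by-visit contrast is the difference in mean change between arms. Let p be the number of mean parameters for change. The ratio of the ML to the REML standard error is √((36 − p)/36). With arm only, p = 2 and the ratio is √(34/36) = 0.972.

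**3. Actual type I error.** The test rejects when |t| exceeds t(0.975; 34) × 0.972 = 2.032 × 0.972 = 1.975. The two-sided tail probability beyond 1.975 on 34 df is 5.64%, so interval coverage is 94.4%. If 36 reference df are used instead of 34, the error is 5.69%.

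**4. Interval and power.** The standard error is 1.20 × √(2/18) = 0.400 kg. The half-width is 2.032 × 0.400 = 0.813 kg with REML and 0.972 × 0.813 = 0.790 kg with ML. Power at 1.15 kg is 79.8% with REML and 81.3% with ML; the extra 1.5 points come from the inflated error rate.

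**5. Does Kenward-Roger repair it?** With complete, balanced data its covariance correction is zero, and a change of degrees of freedom does not rescale a variance that is too small. Simulation of ML with Kenward-Roger (20,000 trials per setting, Monte Carlo SE about 0.16 points, correlations 0.5, 0.8 and 0.95) gave 5.3% to 5.9% with 36 complete cases, and 5.4% to 5.8% with 41 at baseline and 36 at month 3. A larger ML run with the same attrition, using the t(34) critical value (100,000 trials per correlation), gave 5.6% to 5.7%.

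**6. Where it grows.** The same formula with more mean parameters in the tested contrast gives:

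| Model for the change contrast | p | SE ratio | Type I error |
|---|---|---|---|
| Arm only | 2 | 0.972 | 5.6% |
| Change score: arm, baseline VAT | 3 | 0.957 | 6.0% |
| Two visits: age, sex, race each interacting with visit | 5 | 0.928 | 6.8% |
| Change score: arm, baseline VAT, age, sex, race | 6 | 0.913 | 7.2% |

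Race is assumed binary. For the adherence tertile, one third of 36 to 41 is about 12 to 14 participants (assumed to include both arms); with arm only the error is 6.9% at 12 and 6.7% at 14.

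**7. The covariate statements.** Two-visit fits with and without main effects of age, sex and race, on four complete data sets, gave the same arm-by-visit estimate and standard error to six digits. With 41 at baseline and 36 at month 3, four ML fits moved the estimate by about 0.005 to 0.014 kg, and one standard error rose from 0.364 to 0.384. In a change-score model with an unbiased variance, adding baseline VAT only when the arms differ at baseline at p < 0.05 (an assumed rule) gave 4.3% to 4.9%, which is no inflation.

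**The case against.** The strongest reply is that the effect is trivial: 0.6 points of type I error and about 0.02 kg of half-width, in a study that Section II.a calls preliminary and that leaves full quantification to a later trial. No decision is shown to turn on that amount. The figures also come from algebra and hand-written simulation, whereas the plan names SAS 9.3. Both remarks are fair and they limit the weight of the point. They do not remove it, because the stated 0.05 is not what the specified method delivers and the correction costs almost nothing.

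A reader might go further and infer that open covariate selection materially inflates the primary error rate, or that the test will run at 7% or more. The documents do not support that. Section IX.d mainly describes a two-visit model, in which main-effect covariates leave the test unchanged with complete data. The higher figures need either a change-score model, which the plan does not specify, or covariate-by-visit terms, which its unnamed interactions allow but do not establish. Any figure for selection also needs a retention rule and a correlation that the plan does not give. Nor can the baseline tests be charged with inflation: they use no month-3 data, and the version tried did not raise the error. Finally, age, race and sex are not purely discretionary, since one sentence already fixes them.

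**Conclusion.** The point on ML holds and is small. With 18 completers per arm the nominal 5% test runs at about 5.6% and the interval is about 3% too narrow. This assumes approximately normal changes, the arm-only two-visit contrast, and that SAS's Kenward-Roger option behaves as the algebra and simulation indicate. The arm-only figure is near the lower end: it rises to about 6.0% to 7.2% if covariates or covariate-by-visit terms enter the contrast, and to about 6.7% to 6.9% in a tertile of 12 to 14 participants.

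The covariate point is secondary. The sentences conflict and do not define one primary model, but this has no numerical effect on the two-visit test with complete data and only small shifts were seen with the planned attrition. It is a matter of pre-specification, not a demonstrated error in the result.

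**What to change.** In Section IX.d, replace maximum likelihood with REML and keep Kenward-Roger. Apply the same change to the secondary outcomes and the adherence-tertile analysis. With complete data this restores 5.0%.

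Reconcile the covariate sentences by naming one primary model before outcome data are seen: for example, VAT at both visits with arm, visit and arm-by-visit, an unstructured covariance, a fixed covariate list, and the arm-by-visit contrast as the primary test. State which interactions, if any, are included. Whether a covariate stays in the primary model should not depend on the outcome data; other covariate sets can be reported as sensitivity analyses. The descriptive baseline table can stay.

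The cost is a few lines of SAP text and SAS code, with no new data or visits. For the arm-only contrast, the half-width goes from 0.79 to 0.81 kg and nominal power at 1.15 kg from 81.3% to 79.8%. The team also gives up some freedom to change the covariates later.
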